1. PROTOCOL SUMMARY

1.1. Synopsis

Brief Title: A Phase 1 Study to Evaluate the Safety, Tolerability, Immunogenicity and Pharmacokinetics of Single-Dose of PF-06823859 in Japanese Healthy Participants.

Rationale

The purpose of this study is to evaluate the safety, tolerability, immunogenicity and PK of PF-06823859 after single IV administration to Japanese healthy adult participants. The information of safety, tolerability, immunogenicity and PK in Japanese healthy participants is being collected to support the development of PF-06823859 in Japan.

Objectives and Endpoints

Objectives	Endpoints
Primary: 
To evaluate the safety and tolerability of single IV dose of 300 and 900 mg PF-06823859 in Japanese healthy participants.	Primary: 
Assessments of AEs/SAEs including IRR, infusion sites and viral infections, vital signs, ECGs and laboratory tests.
Secondary: 
To evaluate the PK profile of single IV dose of 300 and 900 mg PF-06823859 in Japanese healthy participants.To evaluate the immunogenicity of PF-06823859.	Secondary: 
Serum PF-06823859 PK parameters, as permitted by data: C_{\max}, C_{\max} (dn), T_{\max}, AUC_{inf}, AUC_{inf} (dn), AUC_{last}, AUC_{last} (dn), $AUC_{14\text{day}}$, $AUC_{28\text{day}}$, $t_{1/2}$, CL, V_{ss} and MRT.Incidence of the development of ADA and NAb.

Overall Design

This is a Phase 1, randomized, double-blind, sponsor-open, placebo-controlled study to evaluate the safety, tolerability, immunogenicity and PK of PF-06823859 following a single intravenous dose of PF-06823859 300 and 900 mg in Japanese healthy adult participants.

Number of Participants

Approximately 12 participants are planned to be enrolled into the study. The study consists of 2 cohorts, and approximately 5 participants will be randomized to PF-06823859 and approximately 1 participant will be randomized to placebo in each cohort ([Section 9.5](#)).

Participants who discontinue prior to completion of the study for non-safety related reasons may be replaced at the discretion of the investigator upon consultation with the sponsor.

Intervention Groups and Duration

Within 28 days of successful completion of the screening process, eligible participants will be enrolled and randomized to receive a single IV infusion of PF-06823859 or placebo. The participants in Cohort 2 should be dosed following at least 96 hours safety pause after the participants in Cohort 1 has been dosed. Participants will be admitted into the CRU approximately 1 day prior to dosing and are required to stay overnight in the CRU through completion of Day 5 evaluations. Participants will return to the CRU for outpatient follow-up visits through Day 157.

Data Monitoring Committee or Other Independent Oversight Committee: No

Statistical Methods

Safety and tolerability data will be summarized descriptively through appropriate data tabulations, descriptive statistics, categorical summaries, and/or graphical presentations.

Serum concentrations and serum PK parameters of PF-06823859 will be summarized descriptively.

1.2. Schema

Not applicable.

1.3. Schedule of Activities

The SoA table provides an overview of the protocol visits and procedures. Refer to the **STUDY ASSESSMENTS AND PROCEDURES** section of the protocol for detailed information on each procedure and assessment required for compliance with the protocol.

The investigator may schedule visits (unplanned visits) in addition to those listed in the SoA table, in order to conduct evaluations or assessments required to protect the well-being of the participant.

Visit Identifier ^a Abbreviations used in this table may be found in Appendix 8 .	Screening	CRU Confinement							Follow-Up							ET	
		-28 to -2	-1	1	2	3	4	5	8	15	29	43	57	71	99	127	157
Days Relative to Day 1	-28 to -2	-1															
Visit Window (days)	-	-	-	-	-	-	-	-	±1	±3	±3	±3	±3	±3	±3	±3	-
Hours After Dose			0 ^b	1	2	6	12	24	48	72	96	-	-	-	-	-	-
Informed consent	X																
Demography	X																
CRU confinement		X	→	→	→	→	→	→	→	→	X						
Visit to the CRU	X	X										X	X	X	X	X	X
Inclusion/exclusion criteria	X	X															
Medical/medication history (update)	X	X															
History of illegal drug & alcohol and tobacco use	X	X															
Report prior or concomitant treatments	X	X	→	→	→	→	→	→	→	→	X	X	X	X	X	X	X
Contraception check	X	X									X	X	X	X	X	X	X
Physical exam (including height & body weight at screening, only) ^c	X	X															X
Single 12-Lead ECG	X		X								X		X		X	X	X
Supine BP, PR and oral or axillary temperature	X		X								X		X		X	X	X
Chest X-ray ^d	X																
Serious and nonserious AE monitoring	X	→	→	→	→	→	→	→	→	X	X	X	X	X	X	X	X
Study intervention administration			X ^e														
Safety laboratory (after ≥4 hour fasting) including PT, INR, aPTT	X	X					X			X	X	X	X	X	X	X	X
Viral surveillance (CMV, VZV, EBV, HHV6, HSV-1/2)	X									X	X	X		X		X	X

Visit Identifier ^a Abbreviations used in this table may be found in Appendix 8 .	Screening	CRU Confinement								Follow-Up								ET
		-28 to -2	-1	1		2	3	4	5	8	15	29	43	57	71	99	127	157
Days Relative to Day 1	-28 to -2	-1	1		2	3	4	5	8	15	29	43	57	71	99	127	157	-
Visit Window (days)	-	-	-		-	-	-	-	±1	±3	±3	±3	±3	±3	±3	±3	±3	-
Hours After Dose			0 ^b	1	2	6	12	24	48	72	96	-	-	-	-	-	-	-
FSH in females amenorrheic ≥12 months, only	X																	
Pregnancy test (WOCBP only)	X	X									X		X		X	X	X	X
HIV, HBsAg, HBsAb, HBCab, HCVAb, syphilis	X																	
HBV DNA, if applicable ^f	X															X		X X
Interferon Gamma Release Assay ^g	X																	
COVID-19 questionnaire ^h	X	X									X	X	X	X	X	X	X	X
COVID-19 testing ⁱ	X									X								
COVID-19 check temperature ^j	X	X	X			X	X	X	X	X	X	X	X	X	X	X	X	X
PK blood sampling			X	X ^k	X	X	X	X	X		X	X	X	X	X	X	X	X
Immunogenicity (ADA, NAb) ^l		X									X	X		X	X	X	X	X
CCI																		
Urine drug testing	X	X																
Urinalysis (after ≥4 hour fasting)	X	X						X			X	X	X	X		X	X	X

PFIZER CONFIDENTIAL

Visit Identifier ^a Abbreviations used in this table may be found in Appendix 8 .	Screening	CRU Confinement							Follow-Up							ET			
		-28 to -2	-1	1		2	3	4	5	8	15	29	43	57	71	99	127	157	
Days Relative to Day 1	-28 to -2	-1		1		2	3	4	5	8	15	29	43	57	71	99	127	157	-
Visit Window (days)	-	-		-		-	-	-	-	±1	±3	±3	±3	±3	±3	±3	±3	-	
Hours After Dose			0 ^b	1	2	6	12	24	48	72	96	-	-	-	-	-	-	-	

- a. Day relative to start of study intervention (Day 1).
- b. Pre-dose (except for study intervention administration)
- c. Physical examination may be performed at non-specified timings if there are findings during the previous examination or new/open AEs, if appropriate and at the discretion of the investigator.
- d. Chest X-ray or other appropriate diagnostic image (ie, CT or MRI) results within 12 weeks prior of the screening visit, otherwise a chest X-ray must be performed and results obtained prior to dosing in the study. See [Section 8.2.2](#).
- e. Participants should be monitored from start of study intervention infusion until the end of infusion to assess the infusion site. See [Section 8.2.5](#).
- f. Participants who are HBsAg negative, HBcAb negative and HBsAb positive without unequivocal documentation of prior HBV vaccination or who are HBsAg negative, HBcAb positive and HBsAb positive are required to undergo HBV DNA reflex testing at screening. If HBV DNA is undetectable in the HBV DNA reflex testing at screening and the participant is enrolled the study, HBV DNA testing must be performed on Day 71, 157 and ET. See [Section 8.2.6.1](#).
- g. Additional TB testing is allowed at any time if requested by the investigator and/or if there is a suspicion of TB reactivation or new TB infection. See [Section 8.2.7](#).
- h. Check exposure to positive subject, residence or travel in area of high incidence and COVID-19 related signs and symptoms. To be done at least 2 days before and at each visit.
- i. The testing for COVID-19 pathogen by PCR will be performed between Day -5 and Day -3 to permit availability of test result prior to admission on Day -1. A subsequent COVID-19 test will be performed if they develop COVID-19 like symptom.
- j. To be done at least daily during residence and at every follow-up visit after discharge from the CRU.
- k. End of infusion (ie, 1 hour post-dose)
- l. Participants with positive results may be requested to return for additional follow-up for up to approximately 3 months after final visit.

CCI

2. INTRODUCTION

PF-06823859 is a potent, selective, humanized IgG1 neutralizing antibody directed against the human soluble cytokine IFN β , a member of the type I IFN family of cytokines that is currently being developed for the treatment of SLE with added potential for therapeutic benefit in DM.

2.1. Study Rationale

The purpose of the study is to investigate the safety, tolerability, immunogenicity and PK of PF-06823859 in Japanese healthy adult participants. The information of safety, tolerability, immunogenicity and PK in Japanese healthy participants is being collected to support the development of PF-06823859 in Japan.

2.2. Background

DM is an acquired rare inflammatory disease classified as both a neuromuscular disease and an autoimmune disease. DM is characterized by a distinctive skin rash and muscle weakness or inflamed muscles. Symptoms can come on suddenly or gradually over time. It is thought that the inflammation resulting in cell damage is created when the immune system attacks healthy muscle tissue and blood vessels under the skin. DM is idiopathic; however, some individuals may have a genetic predisposition that is triggered by medications, viruses, bacteria, trauma, toxins, cancer or other illness. DM symptoms often wax and wane for no apparent reason and females are affected twice as often as males.^{1,2}

DM has no known cure and there are no widely approved treatments. Patients typically use a combination of drugs to seek relief for their inflammatory symptoms. Typically, the first line of treatment for the muscle disease is corticosteroids to address the inflammation as well as suppress the immune system. Other immunosuppressive drugs, notably azathioprine, methotrexate, mycophenolate mofetil and cyclophosphamide are used as subsequent lines of therapies in refractory cases or as steroid-sparing agents. However, complications of long-term steroid and immunosuppressive therapies are well documented. Other novel approaches have emerged as potential treatment, including tacrolimus (broadly immunosuppressive drug developed for transplant use), intravenous immunoglobulin, and rituximab, following positive outcomes in some case studies. However, additional randomized controlled trials with these treatments are needed to guide clinical practice.³ Consequently, DM remains a disease with very high unmet medical need, and development of safe and effective therapies is warranted.

2.2.1. Nonclinical Overview

Detailed information concerning the nonclinical studies conducted with PF-06823859 can be found in the SRSD, which for this study is the IB. Overall, these assessments indicate that PF-06823859 is a potent inhibitor of IFN β /IFNAR signaling in human and cynomolgus monkey cells, and the data support the use of the cynomolgus monkey as a pharmacologically relevant species for nonclinical toxicity studies. Furthermore, the nonclinical safety profile of PF-06823859 has been adequately characterized in vitro and in

vivo in cynomolgus monkey to support progression into clinical trials up to 3 months in duration.

2.2.2. Clinical Overview

As of the protocol date, Phase 1, randomized, double-blind, third-party open, placebo-controlled, dose escalating study to evaluate the safety, tolerability, PK and PD of single and multiple IV and SC doses of PF-06823859 in healthy participants (C0251001) has been completed. In addition, Phase 2a, randomized, double-blind, placebo-controlled study to evaluate the efficacy, safety, and tolerability of PF-06823859 in adult participants with DM (C0251002) is ongoing with no data available at this time.

Detailed information concerning the clinical studies conducted with PF-06823859 can be found in the SRSD, which for this study is the IB.

2.2.2.1. Safety

Data from Study C0251001 suggests that PF-06823859 was generally well tolerated and safe when given up to 2000 mg as single IV dose and up to 1800 mg given 600 mg IV Q2W × 3. The most common AE was upper respiratory tract infection, likely due to viral infection. No serious AE or death occurred during the study.

During the SAD period, all TEAEs reported were mild in severity. During the MAD period, while the majority of the TEAEs were mild in severity, 4 TEAEs were moderate in severity: 2 TEAEs (abdominal pain upper and headache) in the placebo SC × 3 doses treatment group, 1 TEAE (upper respiratory tract infection) in the PF-06823859 300 mg SC × 3 doses treatment group and 1 TEAE (sinusitis) in the PF-06823859 600 mg IV (Q4W) × 2 doses treatment group, none of which were considered by the investigator as treatment related.

One participant experienced a mild localized erythema with induration and tenderness after each of the 100 mg SC dosing with PF-06823859 administered Q2W for a total of 3 doses, but no signs or symptoms of a systemic reaction. These local reactions resolved without further intervention within a few days. This participant also had treatment-induced ADA, which had returned to baseline at the time of discharge ([Section 2.2.2.3](#)).

Overall, there was no apparent difference in the total rate of AEs between the participants treated with PF-06823859 compared to placebo and no apparent dose relationship with the doses of PF-06823859. However, the rate of mild upper respiratory tract infection appears to be higher in participants treated with PF-06823859.

There were no clinically significant observations in ECG, vital signs or laboratory abnormalities.

2.2.2.2. Pharmacokinetics

Following single IV administration of 30 mg to 2000 mg doses, PF-06823859 demonstrated a bi-phasic PK profile with a terminal half-life ranging from 22.73 to 29.08 days, slow CL (0.005953 to 0.006817 L/h) and small volume of distribution (4.828 to 6.013 L), all attributes

of a typical IgG1 molecule. Further, T_{max} occurred around 1 hour after the end of the IV infusion, C_{max} ranged from 10.81 to 708.3 $\mu\text{g}/\text{mL}$, and AUC_{inf} ranged from 5042 to 322,100 $\mu\text{g} \cdot \text{h}/\text{mL}$. Both C_{max} and AUC_{inf} showed dose proportional increases across the 30 mg to 2000 mg dose range.

Following multiple IV administration of PF-06823859 at either 600 mg dosing Q2W for a total of 3 doses or 600 mg dosing Q4W for a total of 2 doses, C_{max} and C_{av} after last dose were 284.9 $\mu\text{g}/\text{mL}$ and 181.6 $\mu\text{g}/\text{mL}$ for 600 mg IV Q2W and 259.5 $\mu\text{g}/\text{mL}$ and 109.6 $\mu\text{g}/\text{mL}$ for 600 mg IV Q4W. R_{ac} (based on AUC_{τ}) following 600 mg IV Q2W and 600 mg IV Q4W dosing on Day 29 were 1.893 and 1.407, respectively. R_{ac} , C_{max} (based on C_{max}) was similar with a mean ratio of 1.079 for 600 mg IV Q2W dosing regimen and 1.298 for 600 mg IV Q4W dosing regimen.

Following multiple SC administration of PF-06823859 at either 100 mg or 300 mg dosing Q2W for a total of 3 doses, C_{max} was reached moderately slow with median T_{max} of 96 hours following the first SC dose on Day 1, and slightly earlier at 48 hours after the second dose (Day 15) and the third dose (Day 29), respectively. In addition, C_{max} and C_{av} after last dose were 19.49 $\mu\text{g}/\text{mL}$ and 18.11 $\mu\text{g}/\text{mL}$ for 100 mg SC and 62.92 $\mu\text{g}/\text{mL}$ and 54.26 $\mu\text{g}/\text{mL}$ for 300 mg SC. R_{ac} (based on AUC_{τ}) following 100 mg SC Q2W and 300 mg SC Q2W dosing on Day 29 were 2.376 and 2.499, respectively. R_{ac} , C_{max} (based on C_{max}) was similar with a mean ratio of 2.063 for 100 mg SC Q2W dosing regimen and 2.294 for 300 mg SC Q2W dosing regimen.

2.2.2.3. Immunogenicity

Among all 48 participants treated with PF-06823859 in Study C0251001, 6 participants tested positive for ADA (SAD: 2 participants at 30 mg IV and 1 participant at 900 mg IV; MAD: 1 participant each at 100 mg SC Q2W, 300 mg SC Q2W and 600 mg IV Q2W). Of these 6 participants, 1 participant at 100 mg SC developed treatment induced NAb.

2.3. Benefit/Risk Assessment

A single-dose of PF-06823859 is not expected to provide any clinical benefit to healthy participants. This study is designed primarily to generate safety, tolerability, immunogenicity and PK data for further clinical development.

Nonclinical data to date (Section 2.2.1) has not identified any risk to reproductive organs in sexually mature cynomolgus monkeys, the pharmacologically relevant species. Given that an ePPND study will be conducted later in development, this protocol that allows enrollment of WOCBP has requirements for pregnancy testing (WOCBP only) and use of contraceptives to mitigate unintended exposures.

There is a theoretical risk that alterations in bone may occur based on published observations of osteopenia in mice genetically deficient in IFN β .⁴ The potential for bone effects was assessed in the 3-month GLP toxicity study in sexually mature cynomolgus monkeys, and there were no microscopic findings in bone, nor alterations in circulating bone-related biomarkers. However, the potential for bone effects in developing/growing bones has not

been specifically assessed in growing animals. This risk is considered to be low given the lack of observed effects in the GLP toxicity study as well as the limited duration of total exposure to PF-06823859 in this study. While appropriate risk mitigation has been employed, possible risks will be communicated to study participants in the ICD.

There is a potential risk of increased susceptibility to viral infections with IFN β blockade as with any antagonist of Type 1 interferon signaling (eg, anti-IFNAR1, anti-IFN α , JAK inhibitors). Viral monitoring will be conducted as a precautionary measure to ensure participant safety. Furthermore, during the pandemic, study participants could be infected with the SARS-CoV-2 during study participation. This could lead to increased health risk for this participant and others in the study. Thus, participants must undergo COVID-19 specific assessments according to the [SoA](#).

More detailed information about the known and expected benefits and risks and reasonably expected adverse events of PF-06823859 may be found in the IB, which is the SRSD for this study.

3. OBJECTIVES AND ENDPOINTS

Objectives	Endpoints
Primary: 
To evaluate the safety and tolerability of single IV dose of 300 and 900 mg PF-06823859 in Japanese healthy participants.	Primary: 
Assessments of AEs/SAEs including IRR, infusion sites and viral infections, vital signs, ECGs and laboratory tests.
Secondary: 
To evaluate the PK profile of single IV dose of 300 and 900 mg PF-06823859 in Japanese healthy participants.To evaluate the immunogenicity of PF-06823859.	Secondary: 
Serum PF-06823859 PK parameters, as permitted by data: C_{max}, C_{max} (dn), T_{max}, AUC_{inf}, AUC_{inf} (dn), AUC_{last}, AUC_{last} (dn), AUC_{14day}, AUC_{28day}, $t_{1/2}$, CL, V_{ss} and MRTIncidence of the development of ADA and NAb.

4. STUDY DESIGN

4.1. Overall Design

This is a Phase 1, randomized, double-blind, sponsor-open, placebo-controlled study to evaluate the safety, tolerability, immunogenicity and PK of PF-06823859 in Japanese healthy adult participants.

Approximately 12 participants are planned to be enrolled into the study. The study consists of 2 cohorts, and approximately 5 participants will be randomized to PF-06823859 and approximately 1 participant will be randomized to placebo in each cohort. Participants who discontinue prior to completion of the study for non-safety related reasons may be replaced at

the discretion of the investigator upon consultation with the sponsor. Each participant will receive PF-06823859 or placebo per the scheme summarized in Table 1.

Table 1. Randomization Scheme

Cohort	Treatment	Number of participants
1	PF-06823859 300 mg	5
	Placebo	1
2	PF-06823859 900 mg	5
	Placebo	1

Within 28 days of successful completion of the screening process, eligible participants will be enrolled and randomized to receive a single IV infusion of PF-06823859 or placebo. The participants in Cohort 2 should be dosed following at least 96 hours safety pause after the participants in Cohort 1 has been dosed. Participants will be admitted into the CRU approximately 1 day prior to dosing and are required to stay overnight in the CRU through completion of Day 5 evaluations. Participants will return to the CRU for outpatient follow-up visits per [SoA](#) through Day 157. Participants may be asked to return for additional follow-up visits beyond the anticipated end of study visit for safety reasons and/or at the discretion of the investigator.

ADA levels will be monitored from samples collected at the times specified in the [SoA](#). Samples found to be positive will be further evaluated for NAb. Participants with positive results may be requested to return for additional follow-up for up to approximately 3 months after the last scheduled follow-up visit.

4.2. Scientific Rationale for Study Design

The purpose of this study is to evaluate the safety, tolerability, immunogenicity and PK of PF-06823859 after single IV administration to Japanese healthy adult participants. This study will be randomized, placebo-controlled, double-blinded to treatment assignment in each cohort to permit an unbiased assessment of safety and tolerability.

To date, no safety, immunogenicity and PK data of PF-06823859 in Japanese are available. Although there is no expected relevant PK difference between Japanese and Westerners because monoclonal antibodies are generally known that the absence of ethnic differences in their distribution and elimination, similar to that of endogenous IgG,⁵ it is still important to evaluate safety and characterize PK in Japanese participants before initiating studies in the targeted Japanese patient population.

Single-dose rather than repeated dosing is planned in the study as the steady-state PK can be well predicted from single-dose data. The study duration and frequency of each assessment were decided based on information of Study C0251001.

Assessment of clinical safety laboratory tests (Appendix 2), vital signs, 12-lead ECG, physical examinations, and AE monitoring will provide essential data to evaluate the safety and tolerability of PF-06823859. There is a potential risk of increased susceptibility to viral infections with IFN β blockade as with any antagonist of Type 1 interferon signaling (eg, anti-IFNAR1, anti-IFN α , JAK inhibitors). Viral monitoring will be conducted as a precautionary measure to ensure participant safety.

COVID-19 specific assessments have been incorporated to minimize the risks of COVID-19 related complications to participants and the study site personnel.

4.2.1. Choice of Contraception/Barrier Requirements

Human reproductive safety data are not available for PF-06823859, but there is no suspicion of human teratogenicity based on the intended pharmacology of the compound. Therefore, the use of a highly effective method of contraception is required (see Appendix 4).

4.2.2. Collection of Retained Research Samples

Retained Research Samples will be collected and stored for further analyses which may, for example, provide greater understanding of the study intervention.

4.3. Justification for Dose

The proposed single IV dose levels are 300 mg and 900 mg. These doses are selected based on the safety and tolerability in Study C0251001, CCI [REDACTED]

PF-06823859 doses of 300 mg and 900 mg have been selected to evaluate the safety, tolerability, immunogenicity and PK of PF-06823859 in Japanese healthy adult participants so that safety and tolerability can be examined in the dose range including the maximum potential dose in the planned global late phase studies. CCI [REDACTED]

As described in Section 2.2.2, PF-06823859 repeated IV dose of 600 mg IV Q4W for a total of 2 doses was generally safe and well tolerated in non-Japanese healthy participants in Study C0251001. In addition, R_{ac} (based on AUC_{τ}) and R_{ac} , C_{max} (based on C_{max}) following 600 mg IV Q4W dosing on Day 29 were 1.4 and 1.3, respectively. Considering these results from Study C0251001, exposure following a single 900 mg IV dose is expected to be comparable to steady-state exposure following repeated IV dose of 600 mg IV Q4W.

Based on the above, 300 mg and 900 mg, which CCI [REDACTED] allow the direct comparison of PK with Cohort 3 (300 mg single IV dose) and Cohort 4 (900 mg single IV dose) in Study C0251001 respectively, has been selected as the proposed dose level in the current study.

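### Do second-dose accumulation ratios undermine the claim in Protocol Section 4.3 that a single 900 mg dose is comparable to steady state on 600 mg Q4W?

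*Protocol*

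**What the plan says.** Protocol Section 4.3 supports the dose levels partly by reference to repeated dosing in Study C0251001. It reports that the AUCtau and Cmax accumulation ratios "following 600 mg IV Q4W dosing on Day 29 were 1.4 and 1.3, respectively", and in view of those results states that "exposure following a single 900 mg IV dose is expected to be comparable to steady-state exposure" on 600 mg Q4W.

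The source figures are in Protocol Section 2.2.2.2:
- The regimen was "600 mg dosing Q4W for a total of 2 doses".
- The AUCtau ratios for 600 mg IV Q2W and "600 mg IV Q4W dosing on Day 29 were 1.893 and 1.407, respectively", so the Q4W value is 1.407. The Cmax ratio for Q4W is 1.298.
- Single IV doses gave a "terminal half-life ranging from 22.73 to 29.08 days, slow CL (0.005953 to 0.006817 L/h"), and Cmax and AUCinf "showed dose proportional increases across the 30 mg to 2000 mg dose range".

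Section 4.2 adds that "the steady-state PK can be well predicted from single-dose data".

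Section 4.3 also gives two other visible reasons for the doses: the range includes the maximum potential dose in the planned global late-phase studies, and each dose matches a single-dose cohort of C0251001. Parts of the section are redacted.

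**The concern.** The visible logic is that 900 mg is 1.5 times 600 mg, and 1.5 is close to 1.4 and 1.3. But Day 29 is the second dose of a 28-day regimen, and the half-life is itself about 23 to 29 days. A second-dose ratio then understates accumulation at steady state. For AUCtau the direction reverses: the text suggests that 900 mg slightly exceeds steady state, whereas the protocol's own figures put it below. The sentence also does not say which exposure metric is meant or how close counts as comparable.

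At stake would be how far a clean 900 mg cohort can be said to cover steady-state exposure on 600 mg Q4W in Japanese participants.

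**Working it through.** **Inputs** (all Protocol Section 2.2.2.2): AUCtau ratio 1.407 and Cmax ratio 1.298 for 600 mg Q4W; Cav 109.6 and Cmax 259.5 µg/mL after the second Q4W dose; half-life 22.73 to 29.08 days; CL 0.005953 to 0.006817 L/h; AUCinf, which "ranged from 5042 to 322,100" µg·h/mL over 30 to 2000 mg. The interval is 28 days, or 672 h.

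**1. The plan's own figures.** 1.407 and 1.298 round to 1.4 and 1.3, so they reproduce. The implied comparison is 1.5/1.4 = 1.07 for AUCtau and 1.5/1.3 = 1.15 for Cmax. Neither quotient is printed in the protocol.

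**2. Are these second-dose values?** Let q = exp(−ln2 × 28/t½), which is 0.426 at 22.73 days and 0.513 at 29.08 days. A one-compartment model gives a second-dose ratio 1 + q = 1.43 to 1.51 and a steady-state ratio 1/(1 − q) = 1.74 to 2.05. The observed 1.407 lies near the former.

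**3. AUCtau.**
- Second dose: 109.6 × 672 = 73,651. First dose: 73,651/1.407 = 52,346. Scaled to 900 mg: 52,346 × 1.5 = 78,519 µg·h/mL.
- Superposition: R_ss = 1 + 0.407/(1 − q) = 1.71 to 1.84. Steady-state AUCtau is then 89,448 to 96,097, and the 900 mg ratio is 0.88 to 0.82.
- From 1.407 alone: with linear multi-exponential decline, successive interval AUCs shrink by a factor of at least 0.407, so R_ss ≥ 1/(1 − 0.407) = 1.69 and the ratio is at most 1.5 × 0.593 = 0.89.
- From clearance, which mixes cohorts: 600/0.006817 = 88,015 (R = 1.68, ratio 0.89) and 600/0.005953 = 100,790 (R = 1.93, ratio 0.78). Scaling the 2000 mg AUCinf gives 0.3 × 322,100 = 96,630, ratio 0.81.
- A pure one-compartment model gives 1.5 × (1 − q) = 0.86 to 0.73, but it overpredicts the observed 1.407.

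**4. Cmax.** First dose: 259.5/1.298 = 199.9. At 900 mg: 299.9 µg/mL.
- With the observed increment 259.5 − 199.9 = 59.6, steady state is 199.9 + 59.6/(1 − q) = 304 to 322, ratio 0.99 to 0.93.
- From 1.298 alone, R_ss = 1/(2 − 1.298) = 1.42, ratio 1.05.
- The AUC data imply a different carry-over. The first dose contributes 73,651 − 52,346 = 21,305 µg·h/mL to the second interval. With k = ln2/(24 × t½), the pre-dose level is 21,305 × k/(1 − q) = 47 to 43 µg/mL. Steady state is then 282 to 289, ratio 1.06 to 1.04.

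**5. AUCinf.** Under linear kinetics, steady-state AUCtau of 600 mg equals its single-dose AUCinf, so AUCinf of 900 mg is 900/600 = 1.5 times it.

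**6. How firm are the inputs?** First-dose Cmax for the same 600 mg IV dose is 284.9/1.079 = 264 in the Q2W cohort and 200 in the Q4W cohort, a 32% difference. Superposition would also predict more Cmax accumulation after three Q2W doses than after two Q4W doses. The reported ratios (1.079 and 1.298) go the other way.

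**7. What uses the sentence?** Protocol Sections 9.1 and 9.5 state that there are no hypotheses and no statistical basis for the sample size. SAP Section 6.2.1 summarises PK by treatment and plots dose-normalised parameters. None of these refers to comparability with steady state. The study also reports AUC over 28 days and AUCinf at 900 mg. Under linearity, AUC28day divided by (600/900) × AUCinf gives the ratio in question from Japanese data, without Section 4.3.

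**The case for a change.** The strongest case for a change is that every AUCtau route gives a ratio below 0.90, that none supports 1.07, and that linearity is the protocol's own premise. Redacted text cannot turn a second-dose ratio into a steady-state one, the sentence rests expressly on those ratios, and one or two sentences would correct it. A reader could otherwise credit the 900 mg cohort with matching steady-state AUCtau.

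The core of this stands: the cited ratios do not by themselves show comparability with steady state. The rest carries less weight. Section 4.3 does not call the ratios steady-state values, and the same paragraph gives the two-dose regimen and Day 29. It says only that comparability is expected, with no limit, and an AUCtau shortfall of 11 to 22% (ratios 0.78 to 0.89) can still be described that way, with Cmax about equal and AUCinf higher. The redacted parts might name the metric or give a projection.

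Replacement figures would not be secure either. A floor of 1.69 is already crossed by the clearance route (1.68), the lower end of the AUCtau range moves with the method, and the Cmax ratio falls on either side of 1. Printing such values would exchange a loose phrase for false precision.

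**Conclusion.** No change follows. The Day 29 ratios are second-dose values. On the protocol's figures a single 900 mg dose gives roughly 0.8 to 0.9 of steady-state AUCtau on 600 mg Q4W, about the same Cmax (roughly 0.93 to 1.06), and an AUCinf 1.5 times steady-state AUCtau. These estimates assume linear kinetics, and some combine summary values from different cohorts of C0251001 with no variability stated, so only the direction and approximate size for AUCtau are dependable.

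The sentence is loose background wording that an informed reader can interpret from the numbers beside it. The other visible reasons for the doses are unaffected, nothing here bears on which dose is right, and following the plan as written yields the same data, the same descriptive summaries and a sound conclusion.
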